# **STUDY SUMMARY**

Study Title	Effect of Laryngeal Vibration on Voice Quality
Study Design	Single-intervention, pre- posttest design. Subjects
	perform voice production tasks before, during and
	after vibration.
Primary Objective	The purpose of this research is to examine the
	effects of laryngeal vibration on objective markers
	of speech quality in healthy human volunteers and
	people with spasmodic dysphonia, a voice disorder
	affecting the laryngeal muscles.
Secondary Objective(s)	Obtain preliminary data in a limited sample of SD
	patients that show the potential effectiveness of the
	approach after a single application of vibro-tactile
	stimulation (VTS) of the larynx.
Research	Vibro-tactile stimulation of the superficial skin
Intervention(s)/Investigational	surface above the larynx (human voice box)
Agents	
Scientific Assessment	Nationally based non-federal funding organizations-
	National Spasmodic Dysphonia Association
IND/IDE # (if applicable)	NSR IDE
IND/IDE Holder	N/A
Investigational Drug Services	N/A

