#### 5.2 Study Procedures:

Voice assessment. To assess voice quality, participants will perform two voice production tasks. First, they will vocalize the vowels 'ahh' and 'ee'. They will perform each task three times per assessment. Second, they read aloud twenty test sentences. They will repeat these assessments several times during testing (see Fig. 4). The sentence reading task consists of a set of test sentences based on a 20-sentence inventory described by Ludlow et al. as being sensitive to the voice symptoms experienced in SD [2]. Participants will read the sentences at their own comfortable pace and loudness. In addition, participants will rate their perceived effort level of vocalization on an ordinal scale of 0 to 10 (0 being with no effort and 10 being with maximal effort).

Application of laryngeal vibration. Each VTS trial begins with a 10-second rest period, followed by 4 seconds of vocalization. After 2 seconds of vocalization, vibration will set in while the subject continues to vocalize. Thus, each trial has a rest, a vocalization only, and a vocalization + vibration period. Each participant performs 50 trials per set. The timeline of the complete protocol is illustrated in Figure 4. Testing will begin with a pretest voice assessment, followed by two sets comprising the vibration only and vocalization + vibration conditions. The order of the conditions will be counter-balanced between subjects to account for possible order effects. During the vibration only condition, subjects will be silent and are allowed to read for diversion. After each set a 5-min break will be given and fluids will be offered. Voice assessment batteries will be administered after each set. After completion of two sets and final voice assessments are immediately after treatment (Post 2 OFF), and 20 min and 60 min after VTS has stopped (Post 20, Post 60).

Page 13 of 27

Revised: 9/28/2017

#### Deleted: 4

PROTOCOL TITLE: Effect of Short-term Laryngeal Vibration on Voice Quality. Grant title: Feasibility of laryngeal vibration as a treatment for spasmodic dysphonia 01/31/2021

Figure 2 Experimental design for in-person testing.

Usability questionnaire: The last section of study is to ask participants to fill out a questionnaire about the usability of the wearable collar.

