#### **10.0** Local Number of Participants

10.1 Local Number of Participants to be Consented:

Number of patients with spasmodic dysphonia (SD) will be 20 and number of healthy control subjects (CTL) are 20.

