#### 11.1 Recruitment Process:

Voice-disordered subjects (SD) will be recruited through our own SD patient database, through [name] at the Fairview Lion's Voice Clinic, or through [name] at the Park Nicollet Voice Clinic, St. Louis Park, MN. Control subjects will be recruited from the community via flyer and will be matched for gender and age to the SD participants.

11.2 Identification of Potential Participants:

SD patients are seen regularly by Drs. [name] and [name] as part of their clinical routine. [name] sees approximately 30-40 patients a month and administers Botox injections as medically indicated. Both clinicians will identify potential participants and inform them about the study possibility. The initial contact to potential participants is made by either [name] or [name] at their respective clinics. We will not access patient databases in either clinic to identify potential participants through the study coordinator. Note that potential participants are regularly seen by Drs. [name]/[name] as part of the ongoing patient treatment (e.g. Botox injections). At these scheduled visits Drs. [name]/[name] will share the study information flyer (see ETHOS section: Recruitment Materials) with potential participants and explain to them the scope of the study. If patients are interested in participating, the contact information of the study coordinator will be shared with the patient, who can then contact the study team. Once the study coordinator is contacted by a potential participant, he will explain the study procedure in detail and will invite participation. If agreeable, a date for obtaining informed consent and data collection is set. Prior to study begin, investigators will obtain and document informed consent from each participant according to21 CFR 50, Protection of Human Subjects (see also section 20.0).

Both Drs. [name] and [name] have legitimate access to patient PHI as part of their clinical work. Relevant PHI (type of diagnosis, disease duration, frequency of Botox injections) will not be shared with the study team of the PI before consent has been obtained and the participant has signed the appropriate HIPAA form.

11.3 Recruitment Materials:

Healthy and SD participants will be invited to the study via flyers that summarize the study and its goals.

11.4 Payment:

Study participants will be reimbursed \$100 for one time in-lab study visit. Study participants will be reimbursed \$50 for remote study.

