#### 15.0 Statistical Considerations

#### 15.1 Data Analysis Plan:

Analysis of voice data. Acoustic analysis will follow the methodology described by [50]. Waveform and wide-band spectrograms will be used to identify and measure the duration of the variables. The acoustic signal will be examined for the presence of phonatory breaks and aperiodic breaks. Phonatory breaks are defined as any voiced phonemic segment without sound that is greater than 50ms; the duration of phonatory breaks will be measured. Aperiodic segments will be identified as any voiced phonemic segment that contains non-repetitive cycles that are greater than 50ms; and the duration of the break will be measured. To standardize the duration measures for both phonatory and aperiodic breaks, the sum of the duration of breaks will be divided by the sum of the duration of all voiced segments for each subject. Inter-rater reliability will be measured using Cohen's alpha and intra-rater reliability will use Pearson's r correlation (expected to range between r=.89 to r= .98 according to [50]). For both break types, the absence of phonation or the presence of aperiodicity at the boundary of a syllable or the beginning of a word will not be considered. We will perform a MANCOVA procedure employing all acoustic variables with pre-/posttests as independent factors. If the MANCOVA is significant, separate univariate ANOVAs will be performed on each acoustic variable (dependent) and assessment conditions as a repeated measure (independent) [50]. Appropriate Bonferroni adjustments will account for multiple testing.

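### Condition order is counterbalanced but left out of the analysis model, and balance within the spasmodic dysphonia and control groups is not stated

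*Combined protocol and SAP*

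**What the plan says.** The Study Summary describes the study as "Single-intervention, pre- posttest design". Under section 5.2, the pretest is "followed by two sets comprising the vibration only and vocalization + vibration conditions". The two sets differ in what the participant does: "During the vibration only condition, subjects will be silent and are allowed to read for diversion". On their order, section 5.2 says only this: "The order of the conditions will be counter-balanced between subjects to account for possible order effects". A voice battery follows each set. Further assessments come immediately after the second set and at 20 and 60 minutes.

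Section 10.1 gives the numbers: "Number of patients with spasmodic dysphonia (SD) will be 20 and number of healthy control subjects (CTL) are 20". Section 11.1 says that controls "will be matched for gender and age to the SD participants"; condition order is not among the matching factors.

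Section 15.1 plans a MANCOVA with pre-/posttest as the factor and, if that is significant, "separate univariate ANOVAs will be performed on each acoustic variable (dependent) and assessment conditions as a repeated measure (independent". It names no term for order, condition or diagnosis.

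**The concern.** The protocol expects that order may matter and designs for it, but the analysis does not use the design. Counterbalancing stops order from shifting an average over participants. It does not remove the spread that order creates between them. Only a model term does that.

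The assessment after set 1 is where this bites. At that time some participants have had silent vibration and the others vibration with voicing. If the two conditions change the voice by different amounts, the changes come from two populations with different means, and a model without order counts the gap as noise. The later assessments follow both sets in everyone, so order reaches them only through carry-over.

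The second gap is the level at which balance is promised. Balance between subjects can be met over all 40 participants while the patient and control groups have different mixes of orders. A comparison of the two groups after set 1 would then carry part of the difference between conditions.

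**Working it through.** The documents give no alpha, power, effect size or standard deviation, so there is no planned power figure to reproduce. The inputs are as follows.

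- From the documents: 20 patients and 20 controls (section 10.1); two orders (section 5.2); no order term (section 15.1).
- Assumed: two-sided 5% test; after-set-1 change with within-order standard deviation 1; mean change 0.66, which gives about 80% power with order in the model; difference between conditions D = 0.5, 0.8 or 1.0; patients split 10:10.
- Simplification: a test of the mean change from pretest to after set 1 in the patient group, not the full repeated-measures ANOVA.

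**Step 1. Power with order in the model.** The noncentrality is 0.66 × √20 = 2.95. With 18 error degrees of freedom, power is 79.7%, whatever the value of D.

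**Step 2. What omission does to the error estimate.** With a 10:10 split, half the participants lie D/2 above the mean and half D/2 below. The expected estimated variance of change becomes 1 + (D²/4)(20/19). Its square root is:

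- D = 0.5: √1.0658 = 1.032
- D = 0.8: √1.1684 = 1.081
- D = 1.0: √1.2632 = 1.124

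Only the estimate is inflated. With a fixed 10:10 split, the true sampling error of the mean does not change, because the D/2 shifts cancel. Dividing the effect by the inflated standard deviation in a standard power formula gives 77%, 74% and 70%, which overstates the loss. Simulation handles this correctly.

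**Step 3. Power without order, by simulation.**

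| D | Without order | With order |
|---|---|---|
| 0 | 80.0% | 79.7% |
| 0.5 | 78% | 80% |
| 0.8 | 75% | 80% |
| 1.0 | 72% | 80% |

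The loss is about 2, 5 and 8 percentage points. If D = 0, the term costs about 0.2 points: exact power is 79.9% on 19 degrees of freedom and 79.7% on 18.

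**Step 4. Split within diagnosis.** Suppose the orders are balanced 20/20 over all 40 participants and dealt at random (an assumption). The number of patients in one order is then hypergeometric: P(k) = C(20,k) × C(20,20−k) / C(40,20). Summing both tails:

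- 12:8 or worse: 34.3%
- 13:7 or worse: 11.3%
- 14:6 or worse: 2.6%

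The resulting shift in a patient-control contrast after set 1 is D times the difference in order shares. At 12:8 against 8:12 it is (12/20 − 8/20) D = 0.20 D. At 13:7 against 7:13 it is (13/20 − 7/20) D = 0.30 D. With 10:10 in each group it is zero.

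**The case against.** The case on the other side has four parts.

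- **Nobody is allocated to a treatment arm.** Everyone receives both sets in one session, both sets deliver vibration, and the main contrast is within subject. This is right, and it limits the point to the after-set-1 assessment.
- **Section 15.1 names no patient-control contrast.** This is also right. The imbalance in step 4 harms nothing unless that comparison is made. It is foreseeable, because the primary objective covers both groups and controls are matched, but it is not a stated test.
- **D and the 0.66 are assumptions, and at D = 0.5 the loss is only about 2 points.** True. The reply is that the term costs almost nothing if D is zero.
- **Seventeen participants were already recruited by June 2018, according to the Study Summary.** If they count towards the 40, their order cannot be reassigned. The list can apply only to those still to be tested.

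A reader might go further and infer that the next order is predictable, because no random list or concealment is described. The documents are silent on how the order is generated, and counterbalancing can use a random list. Prediction is certain only under a fixed rule such as alternation, which is nowhere stated. A reader might also infer that order lines up with diagnosis, with all patients in one order and all controls in the other. That would need strict patient-control testing in turn. Section 11.1 speaks of matching on gender and age, not of paired testing, and section 20.1 lets participants suggest the date. If the groups were run one after the other, alternation would give 10:10 in each.

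**Conclusion.** The point stands in a limited form. Section 5.2 counterbalances order because order effects are thought possible, and section 15.1 then ignores order. At the after-set-1 assessment this costs about 2 to 8 points of power for D between 0.5 and 1.0, given 20 patients split 10:10 and an assumed change of 0.66 standard deviations. It does not bias the mean change when the split is even.

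The missing statement about balance within groups is a smaller matter. A split of 12:8 or worse has probability 34%, and 13:7 or worse 11%, if orders are dealt at random over all 40. It has consequences only for a comparison of patients with controls after set 1.

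The documents do not show that order is predictable, steered by staff or aligned with diagnosis. They therefore give no ground to require a separate list holder, delayed disclosure of the order, or separate lists for laboratory and remote sessions.

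**What to change.** **Section 15.1.** Add order as a between-subject factor, together with its interaction with assessment. Report the after-set-1 change as the equally weighted average over the two orders. Possible text: *Condition order and the order-by-assessment interaction will be included in the model. The change from pretest to the assessment after set 1 will be estimated within each order and averaged with equal weights.*

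**Section 5.2.** Say how the balance is obtained. Possible text: *For participants still to be tested, condition order will be taken from a computer-generated list in balanced blocks, prepared separately for participants with spasmodic dysphonia and for controls.*

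**Cost.** The first change uses about one error degree of freedom, or about 0.2 points of power if there is no order effect. The second needs two short lists. Neither adds participants, visits or procedures. An incomplete last block, or orders already used, may leave a group slightly off 10:10; the equally weighted estimate allows for that.

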#### **Optional remote testing**

In case a laboratory visits is not feasible, testing will be conducted remotely. Testing consists of a single session and will be conducted via a video call. A high-quality microphone, a voice recorder, the wearable collar, and study and device instruction will be provided to the participant prior to the video call. In addition, participants will download the smartphone application for controlling the device before the video call. The smartphone application is developed for main operating systems which are Android and iOS (for iPhone) and the phone only requires to have Android version 7 or higher, or iOS version 11 or higher for iPhone.

There is no EEG and eye movement recording during the remote testing, and only voice will be recorded using the microphone and the voice recorder that has been shipped to the participant.

At the beginning of the remote session the participant will be instructed to measure the width of their larynx during the video call with study personnel. The study personnel will make sure the measurement in done correctly. Next, the participant will be instructed to move the vibrators and place them apart to the value of measured larynx width from the previous step. Finally, the participant will wear the wearable device in front of the camera. The study personnel via video call will check and make sure the placement is consistent with the study protocol.

The remote testing session will only involve voice recording using the provided microphone and voice recorder. The instruction for using devices is in the package that the participant received before the video call. A study personnel who conducts the study will walk the participant through the instruction and assures that the devices are properly set up before starting the remote testing. The testing follows the following procedure (See Figure 6)

For the baseline assessment, participants will vocalize the vowels 'ahh' and 'ee' each five times and read aloud the 20 test sentences from Appendix A of Ludlow et al. [2]. Participants will read the sentences at their own comfortable pace and loudness. In addition, participants will rate their perceived effort level of vocalization on an ordinal scale of 0 to 10 (0 being

Page 14 of 27

Revised: 9/28/2017

Deleted: 5

PROTOCOL TITLE:	Effect of Short-term Laryngeal Vibration on Voice Quality. Grant
	title: Feasibility of laryngeal vibration as a treatment for
	spasmodic dysphonia
VERSION DATE:	01/31/2021

with no effort and 10 being with maximal effort). This concludes the pretest voice assessment (see Fig. 6). Subsequently, participants will apply the laryngeal vibration on themselves as instructed for a period of 10 minutes. A study personnel will instruct the participant for each step of the testing. The voice assessment will be repeated after each set of VTS and twice during the retention period (see Fig. 6) The procedure for remote testing is identical to the in-laboratory visit except it does not include EEG and eye movement recording.

5 min 5 min 10 min 5 min

Figure 6. Experimental design for remote testing.

The recorded voice data will be stored on the voice recorder that was sent to the participant. The voice data are already deidentified. The audio file names do not contain any HIPPA incompliant information. The files names comprise only the subject ID and the session number (i.e prestest, set 1, etc.). Upon completion of the remote testing session, the participant will receive a prepaid shipping label via email. The participant will print the label and send the equipment back to the laboratory, thus there is no shipping cost for the participant

The stored deidentified voice data will be then removed from the voice recorder and will stored separately on a password protected University of Minnesota HIPAA compliant server where in-laboratory testing data is also located.

Usability questionnaire: The last section of study is to ask participants to fill out a questionnaire about the usability of the wearable collar.

5.3 Study Duration:

The study consists of a single session. Total exposure time to vibration will be approximately 30 minutes. Each VTS set will last 20 minutes. There will be 5 minutes breaks between sets. The interspersed, repeated voice assessment will allow to document time-dependent changes in voice quality and cortical activation due to laryngeal vibration up to 60 minutes past VTS application. Total duration of the study will be 115 minutes.

5.4 Individually Identifiable Health Information:

Page 15 of 27

For SD participants, we collect health information concerning disease duration, and any possible treatment (Botox injection) that they receive and when the last Botox injection had occurred prior to testing. For healthy control participants we only collect initial contact information, but no PHI. The respective HIPAA Agreement Template Form has been uploaded to ETHOS. The PI and his study team have no direct access to any other medical records.

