#### 23.0 Resources Available

23.1 Resources Available:

- We have been collaborating with Drs. [name] and [name] for several years. We are recruiting patients with voice disorders since 2012 and have not had difficulties meeting our recruitment goals.
- As of June 2018 this protocol has been in place for four years. We anticipate to finish work under this current protocol by the end of this year.
- The in-person testing will take place in the Multisensory Perception Laboratory (MSP Lab) in Elliott Hall, University of Minnesota campus. This is a core research facility of the Center for Translational Sensory Science (CATSS). The MSP Lab consists of two rooms, each with a large sound-attenuating chamber for participant testing, and many specialized pieces of equipment (see below). The MSP Lab is a shared research space and is available to groups throughout the University of Minnesota community, as well as industry groups associated with CATSS.
- The MSP Lab is not a clinical entity. No physicians or licensed psychologists are on staff. If participants require medical help because of an anticipated or unanticipated event during participation, investigators will have to notify emergency services through a 911 call.
- All study personnel has been trained to perform their respective function according to the protocol. They are aware of their duties for informing participants and for obtaining consent. They all have received the necessary human subject protection training as required by University policies.

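### Testing mode follows visit feasibility, differs in procedure and is absent from the 15.1 model, so two procedures are pooled and any patient-control comparison can be confounded

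*Combined protocol and SAP*

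**What the plan says.** Mode of testing is decided by circumstance (protocol, Optional remote testing): "In case a laboratory visits is not feasible, testing will be conducted remotely". No section balances, caps or stratifies mode.

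The two groups reach the study by different routes (section 11.1). For patients: "Voice-disordered subjects (SD) will be recruited through our own SD patient database", or through two voice clinics. For controls: "Control subjects will be recruited from the community via flyer and will be matched for gender and age to the SD participants". Mode is not a matching variable. Section 10.1 plans 20 participants in each group.

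On set order, section 5.2 says: "The order of the conditions will be counter-balanced between subjects to account for possible order effects". It does not say whether this is done within diagnosis or within mode.

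On analysis, section 15.1 says: "We will perform a MANCOVA procedure employing all acoustic variables with pre-/posttests as independent factors". The follow-up univariate ANOVAs use assessment condition as the only stated factor. Neither model names a mode term, a diagnosis term or a covariate.

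The remote-testing section states that its procedure matches the laboratory visit in everything except EEG and eye-movement recording.

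**The concern.** The claim that the modes are equivalent does not agree with the procedures the protocol describes. If those differences alter how much the voice measures change, two consequences follow.

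First, the pre-post estimate in 15.1 becomes a weighted average of two procedures, with the weights set by who happened to be able to visit.

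Second, a comparison of patients with controls would carry part of the mode effect whenever the remote share differs between the groups. The primary objective includes effects on markers "of speech quality in healthy human volunteers and" people with spasmodic dysphonia, and controls are matched to patients, so such a comparison is implied. EEG is recorded only in person, so any EEG comparison is confined to those who could attend, and the gender and age matching may not survive in that subset.

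**Working it through.** **1. No figure to reproduce.** The documents give no remote share, mode effect, effect size, variance, alpha level or power. What follows combines a comparison of the text with illustrations on stated assumptions.

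**2. The two modes side by side.**

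| Item | In person | Remote |
|---|---|---|
| Vowel repetitions | three per assessment (5.2) | five each at baseline |
| Vibration period | 20-minute sets (5.3, which names no mode) | 10 minutes, self-applied |
| Vibrator positioning | study personnel (4.1) | participant, checked by personnel on video |
| Recording | laboratory rooms, "each with a large sound-attenuating chamber for participant testing" (23.1) | shipped microphone and recorder |
| EEG | yes (5.1) | none |

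Because 5.3 names no mode, the 10 against 20 minutes is either a real difference between modes or a drafting conflict. The trial structure in 5.2 does not settle it: 50 trials x (10 + 4) s = 700 s, about 11.7 minutes, which is neither figure. The timeline figures are not available here.

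**3. Pooled estimate.** With remote share p, pooled change = (1 - p) x laboratory change + p x remote change. Assume p = 0.5, laboratory change 1 and remote change 0.5. The result is 0.5 x 1 + 0.5 x 0.5 = 0.75.

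**4. Group contrast, same mode effect in both groups (assumed).** Bias = (remote share in patients - remote share in controls) x (remote change - laboratory change). Keeping the assumed changes of 1 and 0.5:
- 50% against 10% remote: patients 0.75, controls 0.95, gap 0.20 of the laboratory change.
- 60% against 0%: patients 0.70, controls 1.00, gap 0.30.
- Equal shares, or no mode effect: gap 0.

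**5. Group contrast, controls hardly change (assumed).** If controls have few breaks to reduce, their change is near 0 in either mode. Patients at 50% remote show 0.75 instead of 1, so the contrast shrinks by 25% whatever mode the controls use. Matching controls on mode would not repair this.

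**6. False-positive rate.** This was simulated with 20,000 two-sample t-tests per scenario. Each had 20 per group, an assumed two-sided alpha of 0.05, no true group difference, and an additive mode effect on the change score. Mode effects are in standard deviations.

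| Remote share, patients / controls | Effect 0.2 | Effect 0.5 | Effect 0.8 | Variance factor with mode in the model |
|---|---|---|---|---|
| 50 / 50 | 0.052 | 0.045 | 0.033 | 1.00 |
| 50 / 25 | 0.053 | 0.057 | 0.070 | 1.07 |
| 50 / 10 | 0.054 | 0.090 | 0.139 | 1.24 |
| 50 / 0 | 0.060 | 0.111 | 0.217 | 1.50 |
| 75 / 10 | 0.067 | 0.164 | 0.331 | 1.76 |
| 100 / 0 | 0.093 | 0.338 | 0.700 | not separable |

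With mode in the model the rate returns to 0.047 to 0.053 wherever the two effects can be separated. For scale, 20 per group detects (1.96 + 0.84) x sqrt(2/20) = 0.89 standard deviations with 80% power.

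The variance factor is 1 / (1 - R²), where R² = (difference in shares)² / [4 x mean share x (1 - mean share)]. For 50 / 10: 0.16 / (4 x 0.3 x 0.7) = 0.190, and 1 / 0.810 = 1.24.

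**The case against.** The strongest reply is that 15.1 plans no patient-control test. The study summary describes a single-intervention pre-post design, and each person is tested once, in one mode. A stable microphone or noise offset therefore largely cancels from that person's change. This stands. Only a mode-dependent change in response matters, for instance through a different exposure or fitting, or through noise that hides breaks and so compresses change. The reply does not remove the pooling of modes within the pre-post estimate.

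A reader might also infer that patients will be tested remotely more often than controls. The documents do not establish that. The disorder is rare, patients are to be seen late in their Botox cycle, and a laboratory visit pays $100 against $50. Those facts make it plausible. On the other side, recruitment is described as local for both groups, the clinics see these patients regularly, and the reach of the patient database is not stated.

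The remote procedure also has safeguards. Staff watch the larynx measurement, check placement and set-up by video, and supply a high-quality microphone. Section 23.1 describes the chambers as facilities, and sections 5.1 and 5.2 do not say that voice is recorded inside them. These points narrow the expected difference between modes. They do not make the procedures the same on repetitions or on who positions the vibrators.

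Finally, the t-test in the simulation is not an analysis in 15.1, and at 50% against 25% the inflation is small (0.053 to 0.070).

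**Conclusion.** The concern holds in conditional form. Mode follows feasibility, nothing balances it between groups, 15.1 omits it, and the statement that the modes are identical conflicts with the protocol's own description. If response differs by mode, the pre-post estimate mixes two procedures. Any patient-control comparison can then be confounded when remote shares differ.

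The illustrative gaps of 0.20 and 0.30 should not be read as the bias in this trial. They rest on three assumptions: the remote shares, a remote change half of the laboratory change, and the same mode effect in both groups. The simulated error rates rest on assumed shares, an assumed alpha and an additive mode effect. Size and direction are unknown and may be zero.

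It would also go too far to say that a planned group test is biased, since 15.1 specifies none, or that set order is unbalanced within groups, since the text is silent. The point is a cheap improvement to the analysis plan.

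**What to change.** - Record the testing mode of each participant and tabulate mode by diagnosis.
- Add mode (between subjects) and mode-by-assessment to the 15.1 models. Mode alone absorbs a difference in level; the interaction carries a difference in change. If patients and controls are to be compared, name that contrast in 15.1 as well.
- Report the in-person-only result as a sensitivity analysis, for each diagnosis. It avoids pooling the two procedures, but describes only those able to attend.
- Counterbalance set order within diagnosis and mode.
- Reconcile sections 5.2, Optional remote testing and 5.3 on vowel repetitions and vibration period with the statement that the procedures are identical.

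**Cost.** No extra participants or visits. Mode takes one degree of freedom. The interaction takes one for a two-level pre/post factor, and one fewer than the number of assessments in the repeated-measures ANOVAs. If mode is unbalanced, the variance of a group contrast rises, for example 1.24-fold at 50% against 10% remote. At 100% against 0% no model can separate the effects, so the mode-by-diagnosis table should be watched during recruitment.

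Testing each control in the matched patient's mode is optional. It balances mode between the groups without that variance cost, but sacrifices EEG: if half the patients were remote, 0.5 x 20 = 10 controls would give none. It would not undo the dilution in step 5 of the working.
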